Appendix C: Declaration of Helsinki

This clinical investigation will be conducted under the guidance of the current Declaration of Helsinki, which can be found at the following website:

<http://www.wma.net/en/20activities/10ethics/10helsinki/>.

Appendix E: Report of Priors

[REDACTED]

[REDACTED]

[REDACTED]

Appendix F: Amulet Product Labeling/Instructions for Use (IFU)
[REDACTED]

Appendix G: Physician Training Plan

[REDACTED]

Appendix H: Case Report Forms

[REDACTED]

Appendix I: Modified Rankin Scale

Subject Identifier: _____

Rater Name: _____

Date: _____

Score	Description _____
0	No symptoms at all
1	No significant disability despite symptoms; able to carry out all usual duties and activities
2	Slight disability; unable to carry out all previous activities, but able to look after own affairs without assistance
3	Moderate disability; requiring some help, but able to walk without assistance
4	Moderately severe disability; unable to walk without assistance and unable to attend to own bodily needs without assistance
5	Severe disability; bedridden, incontinent and requiring constant nursing care and attention
6	Dead

TOTAL (0-6): _____**Comments:**

Appendix J: The Barthel Index
[REDACTED]

Appendix K: CHADS₂ score & CHA₂DS₂-VASc score

The CHADS₂ scoring system criteria is specified below:

CHA₂DS	Score
Congestive heart failure	1
Hypertension	1
Age \geq 75	1
Diabetes mellitus	1
Stroke/TIA	2

The CHA₂DS₂-VASc scoring system criteria is specified below:

CHA₂DS₂-VASc	Score
Congestive heart failure/LV dysfunction	1
Hypertension	1
Age \geq 75	2
Diabetes mellitus	1
Stroke/TIA/TE	2
Vascular disease [prior myocardial infarction, peripheral artery disease or aortic plaque]	1
Age 65-74	1
Sex category [i.e. female gender]	1

Appendix L: HAS-BLED score

The HAS-BLED scoring system criteria is specified below:

HAS-BLED	Score
Hypertension history (uncontrolled, > 160 mmHg systolic)	1
Abnormal renal function/renal disease (dialysis transplant, creatinine > 2.6 mg/dL or > 200µmol/L)	1
Liver disease (cirrhosis, bilirubin > 2x normal AST/ALT/AP > 3x normal)	1
Stroke history	1
Bleeding, anemia, or predisposition to bleeding	1
Labile INR (Unstable/high INRs, or poor time (< 60% time in therapeutic range))	1
Elderly - Age \geq 65 years	1
Drugs - Medication usage predisposing to bleeding (antiplatelet agents, NSAIDs)	1
Alcohol usage history (> 8 drinks/week)	1

Appendix M: Bleeding Academic Research Consortium Definitions (BARC)⁵²

All bleeding events will be classified according to the BARC definitions.

Bleeding

Classified as Type 0 – 5 according to the following BARC definitions

Type 0: No bleeding

Type 1: Bleeding that is not actionable and does not cause the patient to seek unscheduled performance of studies, hospitalization, or treatment by a healthcare professional; may include episodes leading to self-discontinuation of medical therapy by the patient without consulting a healthcare professional

Type 2 (minor): Any overt, actionable sign of hemorrhage (e.g. more bleeding than would be expected for a clinical circumstance, including bleeding found by imaging alone) that does not fit the criteria for Type 3, 4, or 5 but does meet at least one of the following criteria: (1) requiring nonsurgical, medical intervention by a healthcare professional, (2) leading to hospitalization or increased level of care, or (3) prompting evaluation

Type 3 (major):

Type 3a:

- Any transfusion with overt bleeding
- Overt bleeding plus a hemoglobin drop of ≥ 3 to < 5 g/dL (provided hemoglobin drop is related to bleeding)

Type 3b:

- Overt bleeding plus hemoglobin drop ≥ 5 g/dL (provided hemoglobin drop is related to bleed)
- Cardiac tamponade
- Bleeding requiring surgical intervention for control (excluding dental/nasal/skin/hemorrhoid)
- Bleeding requiring intravenous vasoactive drugs

Type 3c:

- Intracranial hemorrhage including subdural hemorrhages (does not include microbleeds or hemorrhagic transformation, does include intraspinal)
- Subcategories confirmed by autopsy or imaging or lumbar puncture
- Intraocular bleed compromising vision

Type 4: Coronary artery bypass graft (CABG)–related bleeding:

- Perioperative intracranial bleeding within 48 hours
- Reoperation after closure of sternotomy for the purpose of controlling bleeding

- Transfusion of ≥ 5 units whole blood or packed red blood cells within a 48-hour period (only allogenic transfusions are considered transfusions for CABG-related bleeds)
- Chest tube output ≥ 2 L within a 24-hour period

Notes: If a CABG-related bleed is not adjudicated as at least a type 3 severity event, it will not be classified as a bleeding event. If a bleeding event occurs with a clear temporal relationship to CABG (i.e. within a 48-hour timeframe) but does not meet type 4 severity criteria, it will not be classified as a bleeding event.

Type 5: Fatal bleeding

Fatal bleeding is bleeding that directly causes death with no other explainable cause.

BARC fatal bleeding is categorized as either definite or probable as follows:

Type 5a:

Probably fatal bleeding: bleeding that is clinically suspicious as the cause of death, but the bleeding is not directly observed and there is no autopsy or confirmatory imaging

Type 5b:

Definite fatal bleeding: bleeding that is directly observed (by either clinical specimen [blood, emesis, stool, etc.] or imaging) or confirmed on autopsy

The site of fatal bleeding is specified as intracranial, gastrointestinal, retroperitoneal, pulmonary, pericardial, genitourinary, or other.

Bleeding Academic Research Consortium (BARC) indicates fatal bleeding is meant to capture deaths that are directly due to bleeding with no other cause. The time interval from the bleeding event to the death should be considered with respect to likely causality, but there is no specific time limit proposed. Bleeding that is contributory but not directly causal to death is not classified as fatal bleeding but may be categorized as other forms of bleeding. Bleeding that leads to cessation of antithrombotic or other therapies may be contributory but again would not be classified as fatal bleeding.

Appendix N: Echo Acquisition Protocol
[REDACTED]

Appendix O: Additional Definitions

- **Technical success:** Exclusion of the LAA with no device-related complications and no leak >5mm on color Doppler TEE⁵³
- **Procedural success:** Technical success with no procedure-related complications, except for uncomplicated (minor) device embolization⁵³
- **Device success:** Device deployed and implanted in correct position⁵³
- **Device-related complication:** Adverse events which are adjudicated as device-related and require either an invasive surgical or percutaneous intervention. Examples of device-related complications may include embolization requiring percutaneous/surgical intervention, pericardial effusion or cardiac tamponade requiring pericardiocentesis or surgery, device-related infection, etc.
- **Procedural complication:** Adverse events which are adjudicated as procedure-related and require either an invasive surgical or percutaneous intervention. Examples of procedural complications may include embolization requiring percutaneous/surgical intervention, pericardial effusion or cardiac tamponade requiring pericardiocentesis or surgery, etc.
- **Major vascular complication:**⁵⁴
 - Any aortic dissection, aortic rupture, annulus rupture, left ventricle perforation, or new apical aneurysm/pseudo-aneurysm
 - Access site or access-related vascular injury (dissection, stenosis, perforation, rupture, arterio-venous fistula, pseudoaneurysm, hematoma, irreversible nerve injury, compartment syndrome, percutaneous closure device failure) leading to death, life-threatening or major bleeding, visceral ischemia, or neurological impairment
 - Distal embolization (non-cerebral) from a vascular source requiring surgery or resulting in amputation or irreversible end-organ damage
 - The use of unplanned endovascular or surgical intervention associated with death, major bleeding, visceral ischemia or neurological impairment
 - Any new ipsilateral lower extremity ischemia documented by patient symptoms, physical exam, and/or decreased or absent blood flow on lower extremity angiogram
 - Surgery for access site-related nerve injury
 - Permanent access site-related nerve injury

- **Stroke:**⁵³ An acute episode of focal or global neurological dysfunction caused by brain, spinal cord, or retinal vascular injury as a result of hemorrhage or infarction. The event classifies as a stroke rather than a TIA based on any of the following:
 - Duration of neurological dysfunction >24 h[ours]
 - Duration of neurological dysfunction <24 h[ours] in case of imaging-documented new hemorrhage or infarction
 - A neurological dysfunction resulting in death
- **TIA:**⁵³ Any neurological dysfunction not satisfying the above criteria for stroke, specifically if lasting ,24 hours without imaging-documented acute brain infarction
- **Systemic embolism:**⁵³ Acute vascular insufficiency or occlusion of the extremities or any non-CNS organ associated with clinical, imaging, surgical/autopsy evidence of arterial occlusion in the absence of other likely mechanism (e.g. trauma, atherosclerosis, or instrumentation). When there is presence of prior peripheral artery disease, angiographic or surgical or autopsy evidence is required to show abrupt arterial occlusion.
- **AF classification**⁵⁵
 - **Paroxysmal AF** – AF that terminates spontaneously or with intervention within 7 days of onset. Episodes may recur with variable frequency.
 - **Persistent AF** – Continuous AF >7 days in duration
 - **Permanent AF** – AF that cannot be corrected. The term “permanent AF” is used when the patient and clinician make a joint decision to stop further attempts to restore and/or maintain sinus rhythm. Acceptance of AF represents a therapeutic attitude on the part of the patient and clinician rather than an inherent pathophysiological attribute of AF. Acceptance of AF may change as symptoms, efficacy of therapeutic interventions, and patient and clinician preferences evolve.

Appendix P: QVSFS

1.0 INTRODUCTION

[figure not shown]
This document is a statistical analysis plan for the AMPLATZER[™] Amulet[™] Left Atrial Appendage Occluder Randomized Controlled Trial (refer to CIP **F** for the clinical investigational plan).

2.0 TRIAL OBJECTIVES

The objective of this clinical trial is to demonstrate that the safety and effectiveness of the Amulet device is non-inferior to that of the Boston Scientific LAA closure (LAAC) device in subjects with non-valvular atrial fibrillation. The trial will test whether the device meaningfully improves health outcomes through evaluation of the primary safety endpoint, primary effectiveness endpoint, and mechanism of action endpoint. The intended patient population for this trial would be those already indicated for the Control device, therefore, a randomized device-to-device comparator trial is appropriate for evaluating the outcomes of those with non-valvular atrial fibrillation and an increased risk of stroke.

3.0 TRIAL DESIGN

This is a prospective, randomized, multi-center active control trial intended to demonstrate noninferiority of the Amulet device to the commercially available Boston Scientific LAAC device in subjects with non-valvular atrial fibrillation.

The trial is expected to take approximately 3 years to enroll, and each subject will be followed for 5 years. Follow-up visits may occur as part of a post-approval study, should the Amulet device gain approval for commercial distribution prior to the subject's 5-year visit.

Statistical Analysis Plan

The trial will utilize a Clinical Events Committee (CEC) to review adverse events for adjudication of trial endpoints.

4.0 TRIAL ENDPOINTS

4.1 Primary Safety Endpoint

The primary safety endpoint is a composite endpoint of CEC adjudicated procedure-related complications (refer to Appendix P in the CIP for definition), or all-cause death or major bleeding (defined as Type 3 or greater based on the Bleeding Academic Research Consortium (BARC) definition) through 12 months.

4.2 Primary Effectiveness Endpoint

The primary effectiveness endpoint is a composite endpoint of ischemic stroke or systemic embolism through 18 months.

4.3 Mechanism of Action Primary Endpoint

Device closure (defined as residual jet around the device ≤ 5 mm) at the 45-day visit documented by transesophageal echocardiogram (TEE/TOE) defined by Doppler flow.

4.4 Secondary Endpoints

The trial has the following secondary endpoints:

- A composite of all stroke, systemic embolism, or cardiovascular/unexplained death through 18 months
- Major bleeding rate through 18 months (defined as Type 3 or greater based on BARC definition)
- A composite of procedure-related complications, or all-cause death, or major bleeding through 12 months (superiority analysis)
- A composite of ischemic stroke or systemic embolism through 18 months (superiority analysis)
- Device closure (defined as residual jet around the device ≤ 5 mm) at the 45-day visit documented by TEE/TOE, defined by Doppler flow (superiority analysis)

4.5 Descriptive Endpoints

The trial has a number of descriptive endpoints. See Section 5.3 for a full listing.

Statistical Analysis Plan

5.0 STATISTICAL METHODS

5.1 Primary Endpoints

This trial has one primary safety endpoint, one primary effectiveness endpoint, and one mechanism of action primary endpoint.

5.1.1 Primary Safety Endpoint

The primary safety endpoint is a composite endpoint of procedure-related complications, or allcause death or major bleeding (defined as Type 3 or greater based on the Bleeding Academic Research Consortium (BARC) definition) through 12 months. The primary safety endpoint will be reported and analyzed based on event adjudication by the CEC.

5.1.1.1 Hypothesis

Let p_1 (Amulet) be the probability of a primary safety endpoint event with the Amulet device, while p_1 (Control) is the corresponding probability with the Control device. The following hypothesis will be tested:

H₀: $p_1(Amulet) - p_1(Control) \ge \Delta_1$

H₁: $p_1(Amulet) - p_1(Control) < \Delta_1$

where Δ_1 is the absolute value of the non-inferiority margin for the safety endpoint.

Ver. A

Study Name: AMPLATZER[™] Amulet[™] Left Atrial Appendage Occluder Randomized Controlled Trial

Ver. A

Study Name: AMPLATZER[™] Amulet[™] Left Atrial Appendage Occluder Randomized Controlled Trial

Statistical Analysis Plan

5.1.2 Primary Effectiveness Endpoint

The primary effectiveness endpoint is a composite endpoint of ischemic stroke or systemic embolism (SE) through 18 months.

[figure not shown]
5.1.2.1 Hypothesis

Let p_2 (Amulet) be the probability of a subject experiencing a primary effectiveness endpoint event in the Amulet group, while p_2 (Control) is the corresponding probability in the Control group. The following hypothesis will be tested:

 $H_0: p_2(Amulet) - p_2(Control) \ge \Delta_2$

H₁: $p_2(Amulet) - p_2(Control) < \Delta_2$

[figure not shown]
where Δ_2 is the absolute value of the non-inferiority margin for the effectiveness endpoint.

[figure not shown]

Ver. A

Study Name: AMPLATZER[™] Amulet[™] Left Atrial Appendage Occluder Randomized Controlled Trial

Ver. A

_

Ver. A

Study Name: AMPLATZER[™] Amulet[™] Left Atrial Appendage Occluder Randomized Controlled Trial

Statistical Analysis Plan

5.1.3 Mechanism of Action Primary Endpoint

The primary endpoint of device closure is the device closure rate at the 45-day visit. Device closure is defined as residual jet around the device ≤ 5 mm, documented by TEE/TOE. Closure will be determined by Doppler flow and adjudicated by an independent Echocardiography Core Laboratory.

Ver. A

Study Name: AMPLATZER[™] Amulet[™] Left Atrial Appendage Occluder Randomized Controlled Trial

Statistical Analysis Plan

[figure not shown]
5.1.3.1 Hypothesis

Let p_3 (Amulet) be the 45-day closure probability in the Amulet group, while p_3 (Control) is the corresponding probability in the Control group. The following hypothesis will be tested:

 $H_0: p_3(Amulet) - p_3(Control) \le -\Delta_3$

[figure not shown]
H₁: $p_3(Amulet) - p_3(Control) > -\Delta_3$

where Δ_3 is the absolute value of the non-inferiority margin.

Statistical Analysis Plan

5.2 Secondary Endpoints

The following secondary endpoints will be tested if the primary safety and effectiveness noninferiority null hypotheses are both rejected:

[figure not shown]
5.2.1 Composite endpoint of all stroke, systemic embolism, or cardiovascular/unexplained death through 18 months

The following hypothesis will be tested:

 $H_0: p_4(Amulet) - p_4(Control) \ge \Delta_4$

H₁: $p_4(Amulet) - p_4(Control) < \Delta_4$

where p_4 (Amulet) and p_4 (Control) are the probabilities of subjects in the two groups experiencing a composite endpoint of all stroke, systemic embolism, or cardiovascular (CV)/unexplained death through 18 months and Δ_4 is the absolute value of the non-inferiority margin.

5.2.2 Major bleeding through 18 months

The following hypothesis will be tested:

 $H_0: p_5(Amulet) - p_5(Control) \ge 0$

Major

Study Name: AMPLATZER[™] Amulet[™] Left Atrial Appendage Occluder Randomized Controlled Trial

Statistical Analysis Plan

 $H_1: p_5(Amulet) - p_5(Control) < 0$

where p5(Amulet) and p5(Control) are the 18-month major bleeding probabilities in the two groups

bleeding is defined as Type 3 or greater based on the BARC definition.

5.2.3 Superiority test of the primary safety endpoint

If non-inferiority of safety of Amulet over control is demonstrated, a reflex test for superiority will be performed to determine if the Amulet device is superior to the Control device. The hypothesis is as follows:

 $H_0: p_1(Amulet) - p_1(Control) \ge 0$

 $H_1: p_1(Amulet) - p_1(Control) < 0$

The hypothesis will be tested at the 2.5% significance level.

5.2.4 Superiority test of the primary effectiveness endpoint

If non-inferiority of effectiveness of Amulet over Control is demonstrated, a reflex test for superiority will be performed to determine if the Amulet device is superior to the Control device. The hypothesis is as follows:

 $H_0: p_2(Amulet) - p_2(Control) \ge 0$

 $H_1: p_2(Amulet) - p_2(Control) < 0$

The hypothesis will be tested at the 2.5% significance level.

Statistical Analysis Plan

5.2.5 Superiority test of device closure rate at the 45-day visit

If non-inferiority of device closure endpoint of Amulet over control is demonstrated, a reflex test for superiority will be performed to determine if the Amulet device is superior to the Control device. The following hypothesis will be tested:

$$H_0: p_3(Amulet) - p_3(Control) \le 0$$

 $H_1: p_3(Amulet) - p_3(Control) > 0$

The hypothesis will be tested at the 2.5% significance level.

5.3 Descriptive Endpoints

The following descriptive endpoints will be summarized by treatment group:

• Technical success rate (refer to Appendix P in the CIP for definition)

The numerator for the event rate is the number of subjects who have technical success. The denominator is the number of subjects having undergone an "implant attempt".

Procedural success rate (refer to Appendix P in the CIP for definition)

The numerator for the event rate is the number of subjects who have technical success with no procedure-related complications except for uncomplicated (minor) device embolization. The denominator is the number of subjects having undergone an "implant attempt".

• Device success rate (refer to Appendix P in the CIP for definition)

The numerator for the event rate is the number of subjects who have a successful implant. The denominator is the number of subjects having undergone an "implant attempt".

Number of subjects on oral anticoagulant at each follow-up visit

The count and proportion of subjects who are on oral anticoagulant at each follow-up visit will be summarized.

Procedure duration

The procedure duration will be summarized using descriptive statistics including mean, standard deviation, median, and range.

Procedural complications by operator

The count and proportion of subjects who have procedural complications will be summarized by operator.

Statistical Analysis Plan

Device thrombosis

The count and proportion of subjects who have device thrombosis will be summarized.

Transient ischemic attack (TIA)

The count and proportion of subjects who experience TIA will be summarized.

• Hemorrhagic stroke

The count and proportion of subjects who experience hemorrhagic stroke will be summarized.

Systemic embolism

The count and proportion of subjects who have systemic embolism will be summarized.

All-cause mortality

The number of deaths will be summarized by frequencies and percentages at 12 months. Kaplan-Meier survival curves will be used to present deaths through longer term follow-up.

Cardiovascular mortality

The number of cardiovascular mortality will be summarized by frequencies and percentages at 12 months. Kaplan-Meier survival curves will be used to present deaths through longer term follow-up.

• Major bleeding, by site and severity (defined as Type 3 or greater based on BARC definition)

The count and proportion of subjects who have major bleeding by site and severity will be summarized.

• Minor bleeding, by site and severity (defined as Type 1 or 2 based on BARC definition)

The count and proportion of subjects who have minor bleeding by site and severity will be summarized.

Ver. A

Study Name: AMPLATZER[™] Amulet[™] Left Atrial Appendage Occluder Randomized Controlled Trial

Ver. A

Study Name: AMPLATZER[™] Amulet[™] Left Atrial Appendage Occluder Randomized Controlled Trial

Ver. A

Study Name: AMPLATZER[™] Amulet[™] Left Atrial Appendage Occluder Randomized Controlled Trial

 _		

Statistical Analysis Plan

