5.2 Study Design and Scope

The Amulet IDE trial is a prospective, randomized, multi-center active control worldwide trial, designed to evaluate the safety and effectiveness of the AMPLATZER Amulet Left Atrial Appendage Occluder. Subjects will be randomized in a 1:1 ratio between the Amulet LAA occlusion device (treatment) or a Boston Scientific LAA closure device (Control).

All enrolled subjects will follow the protocol-required tests and assessments at each scheduled follow-up visit. At US sites or sites where the implanting physicians do not have Amulet implant experience, up to 3 subjects per sponsor-approved implanter may be implanted with the Amulet device prior to randomization as part of the Roll-In Phase, in order to provide initial experience to the site. These data will not be included in the formal endpoint analyses, while data from roll-in subjects at each site will be included in the clinical investigation report and reported to regulatory authorities. All roll-in subjects will have the same data collection and follow-up schedule as randomized subjects.

The trial will be conducted at up to 150 sites worldwide, with up to 100 sites in the US. A majority of subjects will be enrolled in the US. Data collected during this trial will be used

to support approval of the Amulet device in the United States as well as other countries, as needed.

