5.2.1 Number of Required Subjects

A total of 1878 subjects will be randomized to Amulet or Control at up to 150 sites worldwide.

Approximately 343 additional subjects are expected to be enrolled in the Roll-in Phase. Since US implanting physicians have no experience with the Amulet device, up to 3 roll-in subjects per US implanter will result in approximately 343 subjects enrolled in the Roll-in phase (assuming that 40 sites in the US will be initiated under protocol version C, with an average of 2 implanters per site, the total number of roll-in cases for the trial will be approximately 343 subjects: 103 under the previous criteria + 240 under protocol version C).

There is no minimum number of subjects to be enrolled at each site. To ensure enrollment balance across study sites, no investigational site will be permitted to enroll more than 20% of the maximum sample size for the randomized trial.

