9.3 Subject Death

All subject deaths are to be documented and reported to the sponsor within 10 days of becoming aware of the event. A Death eCRF should be completed and include additional information surrounding the death and cause of death. An autopsy may be requested for subjects with an investigational device. Corresponding source documentation (i.e. death certificate, autopsy results, etc.) will be requested, as appropriate.

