14 STATISTICAL CONSIDERATIONS

The following section describes statistical methods for the clinical investigation and justification of the design. Additional details on statistical analyses, including sensitivity analyses, poolability analyses and analysis of descriptive endpoints, are maintained in a separate Statistical Analysis Plan (SAP).

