6.2 Mortality

The number of deaths will be summarized by frequencies and percentages by treatment group at 12 months. Kaplan-Meier survival curves will be used to present deaths through longer term follow-up.

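### If the long-term cardiovascular mortality curve in SAP 5.3 censors non-cardiovascular deaths, one minus Kaplan-Meier overstates absolute risk; cumulative incidence is the better display and costs almost nothing

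*SAP*

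**What the plan says.** SAP 5.3 opens with "The following descriptive endpoints will be summarized by treatment group" and lists all-cause and cardiovascular mortality as separate items. For the cardiovascular item it states: "The number of cardiovascular mortality will be summarized by frequencies and percentages at 12 months. Kaplan-Meier survival curves will be used to present deaths", continuing through longer-term follow-up. The Kaplan-Meier sentence is the same one used for all-cause mortality in that section and for deaths in general in SAP 6.2: "Kaplan-Meier survival curves will be used to present deaths through longer term follow-up".

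No visible text says whether non-cardiovascular deaths are censored, counted or treated as competing events in the cardiovascular curve.

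The horizon is long. SAP 3.0 says that "each subject will be followed for 5 years". Cause of death is available, because Protocol 9.3 says: "A Death eCRF should be completed and include additional information surrounding the death and cause of death". Protocol 14 assigns further detail on descriptive endpoints to the SAP, and part of the SAP after section 5.3 is not visible in the public copy.

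**The concern.** The Kaplan-Meier sentence can be read in two ways.

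- **A cardiovascular curve with other deaths censored.** This is the usual construction, and the item's title and first sentence concern cardiovascular death. A subject who dies of another cause is then treated as still able to die of a cardiovascular cause later. One minus the curve has a valid meaning as net risk under independent censoring. It is not the proportion of subjects who will die of a cardiovascular cause, and it exceeds that proportion whenever non-cardiovascular mortality is above zero. It also does not add up with the all-cause curve in the same section: all-cause risk minus the Kaplan-Meier cardiovascular risk does not give the non-cardiovascular proportion.
- **A curve of deaths from any cause.** Nothing is overstated, but the item repeats the all-cause display and leaves no long-term cardiovascular result.

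At stake is the level of long-term cardiovascular risk reported for each device.

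**Working it through.** The plan states no figure to reproduce, so the check sizes the gap under stated assumptions.

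**Inputs**
- From the documents: "A total of 1878 subjects will be randomized to Amulet or Control" (Protocol 5.2.1) and "Subjects will be randomized in a 1:1 ratio" (Protocol 5.2), so n = 1878/2 = 939 per arm. Follow-up is 5 years (SAP 3.0).
- Assumed, because the documents give no death rates: annual all-cause mortality m of 3-10%, cardiovascular share of deaths s of 40-60%, constant hazards, non-cardiovascular deaths censored.

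**Formulas**
- H = -ln(1 - m)
- One minus Kaplan-Meier: KM = 1 - exp(-s·H·t)
- Cumulative incidence: CIF = s·(1 - exp(-H·t))
- 95% half-width for one arm: 1.96·√(CIF·(1 - CIF)/n)

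**Mid-range example (m = 6%, s = 50%, t = 5).** H = -ln(0.94) = 0.0619.
- KM = 1 - exp(-0.5 × 0.0619 × 5) = 14.33%
- CIF = 0.5 × (1 - 0.94^5) = 0.5 × 26.61% = 13.30%
- Excess: 1.03 points. Half-width: 1.96·√(0.1330 × 0.8670/939) = 2.17 points.
- Additivity: all-cause 26.61% minus 14.33% gives 12.28% non-cardiovascular, where the true figure is 13.30%.

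**Results at 5 years**

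| m | s | KM % | CIF % | Excess (points) |
|---|---|---|---|---|
| 3% | 40% | 5.91 | 5.65 | 0.26 |
| 3% | 50% | 7.33 | 7.06 | 0.27 |
| 3% | 60% | 8.73 | 8.48 | 0.26 |
| 6% | 40% | 11.64 | 10.64 | 1.00 |
| 6% | 50% | 14.33 | 13.30 | 1.03 |
| 6% | 60% | 16.94 | 15.97 | 0.98 |
| 10% | 40% | 19.00 | 16.38 | 2.62 |
| 10% | 50% | 23.16 | 20.48 | 2.68 |
| 10% | 60% | 27.10 | 24.57 | 2.53 |

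Over the same grid the excess is 0.01-0.13 points at 12 months, 0.02-0.29 at 18 months and 0.04-0.50 at 24 months.

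**Against sampling error in one arm, 5 years.** With all 939 followed, the half-widths at m = 10% are 2.37, 2.58 and 2.75 points for shares of 40%, 50% and 60%. The excess equals the half-width at m = 9.36%, 9.76% and 10.56% respectively, the last outside the assumed range. With an effective 80% followed, the half-widths at m = 10% become 2.65, 2.89 and 3.08, and the excess stays below them throughout the range.

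**Between arms, 5 years.** With hazards a (cardiovascular) and b (non-cardiovascular), KM = 1 - exp(-5a) and CIF = a/(a + b)·(1 - exp(-5(a + b))).
- Equal hazards in both arms: no effect on the difference.
- a = 0.025 against 0.03, b = 0.03 in both: KM 11.75% against 13.93% (2.18 points); CIF 10.93% against 12.96% (2.03 points).
- a = 0.03 in both, b = 0.02 against 0.04: KM 13.93% in both (0.00); CIF 13.27% against 12.66% (0.62 points from unrounded values, half-width of the difference 3.04).

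**Simulation check.** 2000 replicates of 939 subjects with both hazards at 0.025 gave a mean KM of 11.75% and CIF of 11.05% at 5 years, against 11.75% and 11.06% from the formulas.

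**The case against.** The strongest reply is that this is an ambiguity, not a demonstrated error.

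- **Censoring is not stated.** Nor does the plan say that one minus the curve will be reported as an absolute risk; the only percentages promised for this item are crude ones at 12 months. This stands, and the point is therefore conditional.
- **The sentence may mean all deaths.** The repeated wording supports that reading, and it carries no overstatement. It then leaves long-term cardiovascular mortality without a display, so the section still needs a change.
- **A rule may sit in SAP text that is not visible.** This cannot be excluded.
- **The effect is small and every rate is assumed.** This is true. The exclusions in Protocol 5.4.2 (life expectancy under 2 years, NYHA class IV, low ejection fraction, severe renal failure) make the top of the range less likely. But the bias runs in one direction, does not shrink with sample size and is avoidable.
- **Kaplan-Meier can give the cleaner device comparison.** With equal cardiovascular hazards and unequal non-cardiovascular hazards, the 0.62-point difference in cumulative incidence comes wholly from the other deaths. This is correct, and it is why the non-cardiovascular incidence should be shown beside the cardiovascular one.
- **Classification of unexplained deaths may matter more.** SAP 5.3 does not say where they go in this item. If, for illustration, 10% of non-cardiovascular deaths moved to the cardiovascular group, the mid-range 5-year figure would shift by 0.10 × 13.30 = 1.33 points, more than the 1.03-point excess. This is a useful addition to the fix, not a reason against it.

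**Conclusion.** The point holds as a minor, conditional one. If non-cardiovascular deaths are censored, the direction of the excess is certain; its size rests on the assumed death rates and constant hazards. It is negligible through 18 months and reaches 0.26-2.68 points at 5 years. It exceeds one arm's sampling error only near the top of the assumed mortality range, and only with nearly complete 5-year follow-up. It affects the reported level of risk more than the comparison of devices. All hypothesis tests, the 12-month percentages and the all-cause curve are unaffected. Confidence is medium, because the SAP is only partly visible and the sentence has a second reading.

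**What to change.** In SAP 5.3:

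- Keep Kaplan-Meier for all-cause mortality.
- For cardiovascular mortality through longer-term follow-up, present the Aalen-Johansen cumulative incidence by arm, with non-cardiovascular death as a competing event.
- Show the non-cardiovascular cumulative incidence beside it, because each cumulative incidence depends on both death rates. The two then sum to all-cause mortality.
- State which group unexplained deaths fall into for this display.

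The cost is one or two sentences, plus a clause on unexplained deaths, and a standard procedure. Cause of death is already recorded on the Death eCRF, so no data collection, sample size, significance level or test changes. If SAP text that is not public already sets such a rule, a cross-reference from 5.3 is enough.
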